2.8. Primary populations

Baseline data (medical history, concomitant disease (pre-treatment AEs and ongoing medical history, prior medications and therapies, baseline symptoms etc.)) will be presented by treatment group and overall for the ITT population. Baseline and demographics characteristics will be repeated on the safety population if there is at least 10 % difference between the safety and the ITT population

The analysis based on the primary efficacy endpoints will be performed on ITT, mITT and PP populations. mITT and PP analyses will only be considered as exploratory.

The secondary efficacy endpoints will be analysed on the ITT population.

The analyses of safety data will be performed on the safety population.

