3.1.2. Secondary efficacy endpoint(s)

The secondary efficacy endpoints are:

- EFS (defined for each patient as the period of time (in months) from randomisation to time of first clinical disease progression or death from any cause).
- OS (defined for each patient as the period of time (in months) between randomisation and death from any cause).

- Disease-specific mortality (measured as the time (in months) between randomisation and death related to prostate cancer).
- PSADT (defined as the time (in months) from the first documented PSA increase >0.2 ng/mL to the time of the first value more than twice that of the first increased value).
- PSA level at each visit.
- Serum testosterone in the triptorelin treatment group at baseline, 3, 6 and 9 months.
- HRQoL (assessed using the Assessment of Cancer Therapy – Prostate (FACT-P) questionnaire, version 4, and the 36-item short form (SF-36) health survey, version 2) in both treatment arms at baseline, 9, 24 and 36 months.

3.1.3. *Safety endpoint(s)*

The safety endpoints are:

- Signs and symptoms, incidence and severity of all AE(s) regardless of relationship to the study drug graded according to the NCI-CTCAE version 4.0 scale including SAEs and treatment discontinuations due to toxicity.
- Clinical laboratory tests
- Concomitant medications and non-drug therapies
- Concomitant and surgical procedures

3.1.4. *Multiplicity*

No adjustment for multiplicity will be performed.

3.1.5. *Significance testing and estimation*

All statistical tests will be performed two-sided with a type I error rate set at 5%.

Quantitative variables will be summarised in statistical tables indicating the number of non missing observations (n), the mean and standard deviation (SD), the two-sided 95% confidence interval (CI) of the mean, the median, the quartiles (Q1 and Q3), the minimum and maximum.

Qualitative variables will be summarised in statistical tables indicating the number of non missing observations (n), frequency, percentage of each modality and the two-sided 95% CI associated.

For all parameters, the number of missing values will also be reported in the tables, but they will not be counted for the percentage calculation (qualitative data).

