3.2.1.2. Secondary efficacy analysis

The secondary efficacy analyses will be performed on the ITT population. In these analyses, no interaction will be tested for EFS, OS, disease-specific mortality and PSA doubling time. For serum testosterone, only patients in the triptorelin-treated group will be included in the analysis

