3.2.1.2.4. PSA Doubling Time

PSADT will be provided by treatment group (cf. Section 3.2.10 for derived PSADT).
PSADT will be compared between groups using the same analysis and strategy used for BRFS.

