Compliance

Time between first drug administration and RP (weeks) will be derived as $(\text{Date of first drug administration} - \text{Date of radical prostatectomy} + 1) / 7$.

Time between each drug intake (weeks) will be derived as $(\text{Date of drug intake at Visit } t - \text{Date of drug intake at visit } t-1 + 1) / 7$.

Partial dates of treatment will be imputed to calculate times:

- If the day is missing and month is present the 15 of the month will be used.
- If year is present and day and month are missing then the difference between years will be used.

Changes from baseline

Changes from baseline will be calculated as a difference from baseline (e.g. assessment at the visit – assessment at baseline).

Length of patient exposure in the study

Length of patient exposure in the study (months) will be calculated as [(Date of last visit attended – informed consent date) + 1] / 30.4375.

Duration of study drug exposure

Duration of study drug exposure (months) will be calculated as [(Date of last drug administration – Date of first drug administration) / 30.4375] + 3.

Adverse event

Time to onset of AE (days) = AE start date – date of randomisation.

Duration of AE (days) = (AE resolution date – AE start date) + 1.

Time-to-event criteria

BRFS (months) will be derived as (Date of first BR – date of randomisation + 1) / 30.4375.

EFS (months) will be derived as (Date of clinical disease progression or death from any cause – date of randomisation + 1) / 30.4375.

OS (months) will be derived as (Date of death from any cause – date of randomisation + 1) / 30.4375.

Disease specific mortality will be derived as (Date of death related to prostate cancer – date of randomisation + 1) / 30.4375.

PSADT (months) will be derived as (Date of sample when the first PSA value > than twice that of the first increased value – Date of sample of the first PSA value increased value (i.e. > 0.2 ng/mL) + 1) / 30.4375.

All of these time-to-event variables will be rounded to 1 decimal.

For BRFS, EFS, OS and Disease specific mortality, if the date of event or censor is prior to the date of randomisation, the data of event or censor taken into account will be the date of randomisation.

Rules for time-to-event data

The following table defines the rules for censoring data (for Kaplan-Meier analysis)

- BRFS

Event	Decision	Date of event or censor to consider for analysis
BR	Not censored	Date of BR (i.e. date of the first elevated PSA measurement is >0.2 ng/mL*)

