Event	Decision	Date of event or censor to consider for analysis
Clinical disease progression or death from any cause	Not censored	Date of clinical disease progression or death
No clinical disease progression and no death and no premature withdrawal from the study	Censored	Date of last visit
No clinical disease progression no death and patient premature withdrawal from the study or lost to follow-up	Censored	Date of withdrawal from the study or last contact

- OS

Event	Decision	Date of event or censor to consider for analysis
Death from any cause	Not censored	Date of death
Patient alive and no premature withdrawal from the study	Censored	Date of last visit
Patient premature withdrawal from the study or lost to follow-up	Censored	Date of withdrawal from the study or last contact

- Disease-specific mortality

Event	Decision	Date of event or censor to consider for analysis
Death related to prostate cancer	Not censored	Date of death
Death not related to prostate cancer	Censored	Date of death
Patient alive and no premature withdrawal from the study	Censored	Date of last visit
Patient premature withdrawal from the study or lost to follow-up	Censored	Date of withdrawal from the study or last contact

- PSADT

Event	Decision	Date of event or censor to consider for analysis
First PSA value > than twice that of the first increased value (> 0.2 ng/mL)	Not censored	Date of sample when the first PSA value > than twice that of the first increased value
No PSA value 2 times higher than the first increased value or no increased value and no premature withdrawal from the study	Censored	Date of last evaluable sample
Patient premature withdrawal from the study or lost to follow-up	Censored	Date of last evaluable sample before withdrawal from the study or last contact

Incomplete dates for time-to-event analyses will be handled as follows:

- If the day of the randomisation is missing and month is present, the 15 of the month will be used.
- If the day of the BR, clinical progression or death is missing and month is present, the 01 of the month will be used.
- If the month (or the date) of the death is missing, the date of the last contact will be used.
- The other dates with missing month will be studied case by case.

Castrated patients

A patient will be considered as:

- Castrated if the testosterone level is inferior to 50 ng/dL for the test or confirmation test.

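### PSADT has no start date for the roughly 70% of ITT patients expected to have no PSA rise, yet the SAP censors them and asks for an ITT comparison

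*SAP*

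**What the plan says.** Section 3.1.2 measures PSADT "from the first documented PSA increase >0.2 ng/mL to the time of the first value more than twice that" of the first raised value. The formula in Section 3.2.10 agrees: the date it subtracts is the "Date of sample of the first PSA value increased value", meaning above 0.2 ng/mL.

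The PSADT censoring table in the same section has a row for "No PSA value 2 times higher than the first increased value or no increased value and no premature withdrawal from the study". These patients are censored at their last evaluable sample. A further row, for "patient premature withdrawal from the study or lost to follow-up", also censors at the last evaluable sample and does not require that a rise occurred.

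Section 2.8 states that "The secondary efficacy endpoints will be analysed on the ITT population", and Section 3.2.1.2 repeats this. Section 3.2.1.2.4 adds: "PSADT will be compared between groups using the same analysis and strategy used for BRFS". For BRFS, Section 3.2.1.1 specifies log-rank, Kaplan-Meier and Cox.

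The only rule that falls back on the randomisation date begins "For BRFS, EFS, OS and Disease specific mortality, if the date of event or censor is prior to the date of randomisation". It does not name PSADT, and it deals with event or censoring dates that precede randomisation, not with a missing start date.

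**The concern.** A censoring date without a start date gives no duration. The definition, the formula, the censoring table and the ITT requirement therefore cannot all be followed. Two readings are open to a programmer:

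- **Follow the formula.** Patients without a rise get a missing time and drop out. What remains is a comparison of relapsers, a subset selected by an outcome that treatment is expected to change, reported as ITT.
- **Follow the table.** Patients without a rise are listed as censored, so they are given a time, for example from randomisation. Two time origins are then mixed. Each such patient adds a long event-free time, and the triptorelin arm is planned to have more of them. The test can then report slower doubling on triptorelin when it is only restating the BRFS effect.

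Section 1.1.2 names PSADT among the outcomes on which the groups are to be compared, so the result should not depend on an unstated choice.

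**Working it through.** **Planning inputs (SAP Section 1.3.4).** 113 patients per arm; 36-month relapse 40% v 20%; two-sided 5% log-rank test, 90% power; dropout about 5% per year; 61 BR events.

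**The plan's own figure.** HR = ln(0.80)/ln(0.60) = 0.437. Schoenfeld events = 4 × (1.960 + 1.282)² / (ln 0.437)² = 61.3, and power at 61 events is 89.9%. The stated 61 is reproduced.

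**Patients with no start date.** Confirmed BR is used as a proxy for a rise.

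- No dropout, 36 months: 113 × 0.60 + 113 × 0.80 = 67.8 + 90.4 = 158 of 226 (70%).
- With dropout, P(BR observed) = λ/(λ+d) × [1 − exp(−36(λ+d))], where d = −ln(0.95)/12 = 0.00427 per month. Surveillance: λ = −ln(0.60)/36 = 0.01419, giving 42.2 patients. Triptorelin: λ = −ln(0.80)/36 = 0.00620, giving 21.0. Without BR: 226 − 63.2 = 163 (72%).
- Under the follow-up extension in Section 1.2.2 (simulated): 159-160 (71%).
- At the 61-event cut: 226 − 61 = 165 (73%).
- The PSADT clock needs only a first documented rise, not a confirmed one. If an assumed 5-10% of the 158 have an isolated unconfirmed rise, 70% × 0.95 = 66.5% down to 70% × 0.90 = 63% remain without a start date.

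**What each reading does to the test.** 5,000 simulated trials per scenario (Monte Carlo SE at most 0.7 points): 113 per arm, exponential BR times at the planning rates, 3-monthly sampling, 5% per year dropout. Follow-up is either 36 months for all, or the extension rule with 24-month uniform accrual: patients with BR by month 36 stop at month 36, and the others continue until their own BR or the study's 61st. Doubling times are **identical in both arms**. The SAP gives none, so medians of 6, 10 and 15 months are assumed, exponential or lognormal (log-SD 0.8). Entries are log-rank rejection rates at the 5% level for medians 6/10/15.

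| Patients without a rise | Doubling | 36 months | Extension rule |
|---|---|---|---|
| Timed from randomisation; all relapsers can double | exponential | 79/71/62% | 81/74/63% |
| | lognormal | 80/74/65% | 83/76/65% |
| Timed from randomisation; half of relapsers never double | exponential | 46/39/34% | 47/41/35% |
| | lognormal | 47/43/35% | 47/43/35% |

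In these four rows, rejections against triptorelin occur in at most 0.04% of trials. With no BRFS difference (30% in both arms), timing from randomisation rejects in 4.5-5.4%. Dropping the patients without a rise, or giving them a near-zero time, rejects in 4.4-6.1% in every scenario.

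**Precision of the rise-only set.** About 42 v 21 patients (44 v 22 under the extension rule). Expected doublings are 21-32 v 10-15, or 10-16 v 5-8 if half never double. The 95% limits for the HR lie a factor exp(1.96 × √(1/d₀ + 1/d₁)) either side of the estimate. For 21 v 10, exp(1.96 × √(0.0476 + 0.1000)) = 2.1; for 32 v 15 it is 1.8. In the half-never-double case the factor is about 2.4-2.9, using unrounded mean counts.

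**The case against.** The strongest reply is that the large rejection rates need a reading the SAP never states. The definition and formula give one origin, the first raised sample, and the randomisation-date rule leaves PSADT out. Software given the formula would run and silently drop patients without a rise, and under that reading the test keeps its level. The fix below then yields the same patients and times as the literal formula. PSADT is also one of several secondary endpoints, and the SAS code is redacted and the table shells are not shown; they might state the denominator.

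Much of this stands. The inflation is conditional on timing from randomisation and on a real BRFS effect. The 70% comes from planning rates and is not stated in the SAP. The case in which half never double is an assumption: Section 1.3.1 bars other adjuvant treatment before progression, but says so only for the surveillance arm, so it is weak support.

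What does not fall is the contradiction in visible text. The censoring table expressly includes patients whom the formula excludes, and three sections require ITT. Even the benign reading gives an analysis that is not the one described.

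**Conclusion.** The point holds. The PSADT comparison cannot be carried out on the ITT population as written, because about 70% of patients at planning rates (63-73% across the cases above) have no start date. The consequence depends on an unstated choice: either a comparison of about 42 v 21 relapsers presented as ITT, or a mixed-origin test that rejects in 34-83% of trials with identical doubling if the planned BRFS effect is real. The first figure rests on the SAP's planning rates; the second also rests on assumed doubling times. The fault is confined to a secondary endpoint and leaves the primary BRFS analysis untouched. It should be fixed before PSADT is analysed.

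**What to change.** - **Sections 2.8, 3.2.1.2 and 3.2.1.2.4:** define the PSADT analysis set as ITT patients with a documented PSA above 0.2 ng/mL, timed from that sample, and state that this is an exception to the ITT rule.
- **Section 3.2.10, PSADT table:** delete the clause that admits patients with no increased value, and limit the withdrawal and lost-to-follow-up row to patients with a rise.
- **Reporting:** give the number of patients, the number of doublings and the Kaplan-Meier median with 95% CI per arm. Label any log-rank or Cox comparison exploratory, in a non-randomised subset selected by a post-randomisation outcome.
- **Do not** time patients without a rise from randomisation under the PSADT name. If an ITT comparison is wanted, it needs a separately named endpoint counted from randomisation for every patient, with its own censoring rule.

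The cost is SAP wording in four places and the programming of one secondary endpoint, with no new data. The price is that PSADT will have no ITT p-value, and the rise-only comparison will be imprecise.

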3.2.1.2.6. Serum testosterone

The proportion of castrated (serum testosterone < 50 ng/dL) patients at baseline and 3, 6 and 9 months post-RP will be provided for the triptorelin treatment group. Shift tables between two consecutive visits and between baseline and end of study will be presented of the number and percentage of patients castrated or not.

FACT-P measurements	SF-36v2 measurements

 • Subscales: 
 ○ Physical well-being ○ Social well-being ○ Emotional well-being ○ Functional well-being • Dimensions: 
 ○ General well-being ○ Prostate-specific concerns • Total FACT-P score 	
 • Health Domain Scales: 
 ○ Physical functioning (Raw) ○ Role-Physical (Raw) ○ Bodily Pain (Raw) ○ General Health (Raw) ○ Social Functioning (Raw) ○ Mental Health (Raw) ○ Role-Emotional (Raw) ○ Vitality (Raw) ○ Physical functioning (Norm-based) ○ Role-Physical (Norm-based) ○ Bodily Pain (Norm-based) ○ General Health (Norm-based) ○ Social Functioning (Norm-based) ○ Mental Health (Norm-based) ○ Role-Emotional (Norm-based) ○ Vitality (Norm-based) • Component Summary measures calculated from a combination of norm-based scales scores: 
 ○ Physical Component Summary ○ Mental Component Summary

These HRQoL measurements at baseline and at 9, 24 and 36 months post-RP, will be described using descriptive quantitative statistics for each treatment group (cf. Section 3.2.10 for derived FACT-P and SF-36v2). In addition the change from baseline will also be presented for each of these HRQoL measurements.

For each HRQoL measurement (subscales, dimensions, scales, component summary measures), changes will be analysed using a repeated-measures analysis of covariance using a mixed linear model with patient as a random effect, baseline, group, visit (Month 9, Month 24 and Month 36) and the interaction between group and visit as fixed effects. Correlation structures (auto-regressive (AR(1)), compound symmetry (CS) and unstructured (UN)) will be tested and the best one will be considered for the model (the model with the smaller AIC will be chosen):

Change = baseline + group + visit + group*visit + e

With:

- baseline, group, visit and group*visit as fixed effects,
- e: error $\sim N(0, \sigma e^2)$.

The syntax with SAS using the MIXED procedure will be:

```
CCI [REDACTED]
```

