Laboratory data (haematology, biochemistry) will be listed in SI units and abnormal values will be flagged (High [H], Low [L], clinically significant [C], NCI-CTC grade (G)) where applicable. Any unscheduled laboratory assessments will be flagged [U] in the listings.

For haematology and biochemistry parameters the baseline will be defined as the screening values.

Summary statistics (mean, median, SD and range as appropriate) by treatment group and overall will be presented for clinical laboratory tests at each assessment (screening and 9 month) with change from baseline.

Shift tables will be presented of the number and percentage of patients with below, within or above normal range. For laboratory data, abnormal values will be flagged in the data listings and a list of clinically significant abnormal values will be presented.

In case of available retest sample, values of retest sample will be used instead of the first sample, except at baseline where the last test available before first injection of treatment will be used.

3.2.2.3. *Vital signs*

Descriptive summary statistics will be provided on safety population according to the actual treatment approach followed for vital signs. It includes assessments as detailed in the Section 1.3.2.3 'Vital signs'.

3.2.3. *Missing data and outliers*

3.2.3.1. *Missing data*

Missing data will not be imputed and dropouts will not be replaced.

Rules for missing data imputation for HRQoL will be addressed in 3.2.10 Derived Data.

3.2.3.2. *Missing or incomplete dates*

In all listings, missing or incomplete dates should be left as they have been recorded. However, for calculation / sorting / assignation based on dates, the following methods will be used:

- The most conservative approach will be systematically considered (i.e. if the onset date concomitant medication is missing / incomplete, it is assumed to have occurred during the study treatment phase except if the partial onset date or other data [stop date, ...] indicates differently).
- A missing/incomplete date of medical history or disease diagnosis will be assumed to have occurred before the study inclusion.
- If a partial date and the associated information do not allow to state about the assignation to a group / category, all the possible groups / categories will be considered (i.e.: a medication with partial start and stop dates could be considered as prior and concomitant treatment).

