- Not castrated if the testosterone level is superior or equal to 50 ng/dL for the test and confirmation test.

HRQoL

- FACT-P

The FACT-P score is composed of 27 general questions about physical, social, emotional, and functional well-being as well as a 12-item questionnaire about prostate-specific concerns. A maximum score of 156 points indicates the highest level of QoL. The total FACT-P score will be calculated as the sum of 39 item scores.

Dimensions	Subscales	Number of items	N° item
General well-being	Physical well-being	7	GP1 to GP7
	Social well-being	7	GS1 to GS7
	Emotional well-being	6	GE1 to GE6
	Functional well-being	7	GF1 to GF7
Prostate-specific concerns	--	12	C2, C6 P1 to P8 BL2 to BL5

For missing data, if less than 50 % of the items are missing, subscale scores will be prorated. This will be done by using the formula below:

Prorated subscale score = (Sum of item scores)*(Number of items in the subscale)/
(Number of items answered).

If more than 50 % of the items are missing from any subscale, the subscale will not be imputed.

For any given scale, if the missing values represent more than 10 % of the population; two analyses will be performed. One analysis using the available values and a second analysis imputing the missing values by the mean value of the available data at the concerned timepoint will be performed.

- SF-36v2

The SF-36 health survey version 2 [1] is composed of 36 items about 8 Health Domain Scales: Physical Functioning (PF), Role-Physical (RP), Bodily Pain (BP), Social Functioning (SF), Mental Health (MH), Role-Emotional (RE), Vitality (VT) and General Health (GH).

All but one of the 36 items (item n°2: self-reported health transition) are used to score the eight raw Health Domain Scales. Each item is used in scoring only one scale. The response for each item is recoded according to the table below.

Then, the eight Health Domain Scales Total Raw Scores are calculated, according to the table on the following page. Each score will range from 0 to 100, where 0 represent the lowest possible score (worst health state) and 100 represent the highest possible score (best health state).

Finally, the eight health domain scales scores are normed to the 2009 U.S. general population to have a mean of 50 and a standard deviation of 10. These are health domain scales norm-based scores.

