Two summary measures are calculated, using the eight health domain scales norm-based scores and an algorithm: an overall score of physical health (Physical Component Summary or PCS) and overall score of mental health (Mental Component Summary or MCS)

Item numbers	Precoded response value	Final response value
3a to 3j	1 2 3	3 2 1
2 4a to 4d 5a, 5b, 5c 9b, 9c, 9f, 9g, 9i 10, 11a, 11c	1 2 3 4 5	5 4 3 2 1
7	1 2 3 4 5 6	6 5 4 3 2 1
1 6 8 9a, ,9d, 9e, 9h 11b, 11d	1 2 3 4 5	5 4 3 2 1

Component Summary measures (calculated from a combination of norm-based scales scores)	Health Domain Scales (raw and norm-based)	Number of items	Items
Physical Health (PCS)	Physical functioning (PF)	10	3a to 3j
	Role-Physical (RP)	4	4a to 4d
	Bodily Pain (BP)	2	7, 8
	General Health (GH)	5	1, 11a to 11d
Mental Health (MCS)	Social Functioning (SF)	2	6, 10
	Mental Health (MH)	5	9b, 9c, 9d, 9f, 9h
	Role-Emotional (RE)	3	5a, 5b, 5c
	Vitality (VT)	4	9a, 9e, 9g, 9i

The derivations of the eight Health Domain Scales Total Scores (Raw and norm-based) and the two component summary measures (calculated from a combination of norm-based scales scores) will be performed using software application delivered by QualityMetric.

Missing data are ignored and the scale is calculated without the missing item. If more than 50 % of the items are missing from any scale, the scale score will not be calculated.

For any given value, if the missing values represent more than 10 % of the population; two analyses will be performed. One analysis using the available values and a second analysis imputing the missing values by the mean value of the available data at the concerned timepoint will be performed.

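### The second HRQoL analysis, run when more than 10% of a score is missing, fills gaps with the time-point mean and is not a valid robustness check

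*SAP*

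**What the plan says.** HRQoL is a secondary objective (SAP 1.1.2), measured by FACT-P and SF-36v2 at baseline and months 9, 24 and 36. The HRQoL part of section 3.2.1.2 sets the model: "changes will be analysed using a repeated-measures analysis of covariance using a mixed linear model with patient as a random effect", with baseline, group, visit and group-by-visit as fixed effects.

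Missing scores are handled in section 3.2.10. For FACT-P: "For any given scale, if the missing values represent more than 10 % of the population; two analyses will be performed". The first uses the values that are available; the second works by "imputing the missing values by the mean value of the available data at the concerned timepoint". SF-36v2 has the same rule, opening "For any given value, if the missing values represent more than 10 % of the population; two analyses will be performed".

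Section 3.2.3.1 states the general rule, "Missing data will not be imputed and dropouts will not be replaced", and continues at once: "Rules for missing data imputation for HRQoL will be addressed in 3.2.10 Derived Data".

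Four things are left open: whether the mean is per arm or pooled, whether the 10% is judged per visit, which of the two analyses leads, and how the uncertainty of the filled values enters the standard errors. The point concerns whole missing scale scores. Prorating a partly completed subscale is a separate rule and is not in question.

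**The concern.** Single mean imputation treats a constant as if it were observed data. It lowers the apparent spread and raises the apparent sample size. If the constant is common to both arms, it also pulls the arms together. It ignores the patient's own baseline and earlier scores, which the planned mixed model uses.

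The analysis is called for only when missingness is no longer small, which is when a reader looks to it for reassurance. A diluted difference could then be read as no effect of castration on quality of life, or a falsely narrow interval as a firm one. Because the SAP does not name a leading analysis, nothing says how to treat two results that differ.

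**Working it through.** The SAP gives no figure for the effect of the imputation, so there is none to reproduce. The check has three steps.

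**Inputs.** From the SAP: 113 patients per arm and about 5% dropout per year (1.3.4), two-sided 5% tests (3.1.5), and the 10% trigger (3.2.10). Assumed: a share f missing completely at random and equal in both arms, which is a favourable case for the method.

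**1. Could the trigger be met?** If HRQoL missingness simply followed the planned dropout (an assumption), the missing share would be:
- month 9: 1 − 0.95^0.75 = 3.8%
- month 24: 1 − 0.95^2 = 9.8%
- month 36: 1 − 0.95^3 = 14.3%

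Judged per visit, only month 36 passes 10%. Skipped questionnaires would add to these shares.

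**2. Closed form.** Let n be the number per arm, σ² the residual variance and δ the true difference.

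*Own-arm mean.* The estimate still rests on n(1−f) observed values per arm, so its true variance is 2σ²/[n(1−f)]. Filled values add almost nothing to the residual sum of squares but are counted in n, so the reported variance is about 2σ²(1−f)/n. The ratio of reported to true SE is therefore √[(1−f)²] = 1−f. Coverage is 2Φ(1.96(1−f)) − 1.

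*Pooled mean.* Each arm's mean becomes (1−f) times its own mean plus f times the common mean. The common part cancels, leaving (1−f)δ.

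| f | Own-arm: SE ratio | Own-arm: coverage | Own-arm: type I error | Pooled: share of δ kept |
|---|---|---|---|---|
| 10% | 0.90 | 92.2% | 7.8% | 0.90 |
| 14.3% | 0.857 | 90.7% | 9.3% | 0.857 |
| 20% (assumed) | 0.80 | 88.3% | 11.7% | 0.80 |
| 30% (assumed) | 0.70 | 83.0% | 17.0% | 0.70 |

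**3. Simulation.** 4,000 runs, 113 per arm, ANCOVA of change at one visit, assumed baseline correlation 0.5 and true difference 0 or 0.4 SD. Results are for 10%, 20% and 30% missing, in that order.
- *Own-arm mean, no true difference:* coverage 91.3%, 87.4%, 82.0%. Mean reported SE over actual SD of the estimate: 0.1111/0.1259 = 0.88, 0.1066/0.1355 = 0.79, 0.1007/0.1460 = 0.69.
- *Own-arm mean, true difference 0.4 SD:* the estimate stays at 0.398 to 0.399; coverage 92.4%, 87.8%, 82.8%.
- *Pooled mean, true difference 0.4 SD:* estimate 0.358, 0.319, 0.279; coverage of the true value 93.7%, 88.3%, 77.8%.
- *Pooled mean, no true difference:* type I error 5.4%, 5.5%, 5.2%.
- *Available values only:* estimate 0.398 to 0.400, coverage 94.7% to 95.4%, type I error 5.3%.

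The simulation used a single visit. The three-visit mixed model was not simulated, so the figures show the mechanism and its approximate size, not the exact effect on the planned model.

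**The case against.** The best defence is that the imputed analysis is the second of two. The available-values analysis is always produced, HRQoL is one of several secondary endpoints, and the primary BRFS analysis is untouched. All of this stands and limits the weight of the point. It does not make the second analysis valid.

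A reader might infer more than the documents support:
- *That the HRQoL results as a whole are invalid.* They are not. Mean imputation does not touch the mixed model on available data.
- *That section 3.2.10 contradicts the no-imputation rule in 3.2.3.1.* It does not. The next sentence of 3.2.3.1 refers HRQoL to 3.2.10.
- *That type I error is inflated whichever mean is used.* Only own-arm means inflate it. With a pooled mean the harm is dilution and poor coverage of a true difference.
- *That the SAP specifies a pooled mean.* This is a natural reading, but the text does not say so.
- *That 20% or 30% missing is expected.* These shares are illustrations. The only planning figure is about 5% dropout per year, which gives about 14% at month 36.

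Two further objections shape the remedy. Multiple imputation under missing at random would largely repeat the mixed model's assumption and answer; what adds information is a departure from that assumption. And the mixed model does not rescue a patient with no baseline score. Filling a missing baseline covariate with a mean is a much milder step in a randomised comparison than filling outcomes, so the criticism is confined to post-baseline scores.

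**Conclusion.** The point holds for the second analysis only. Mean imputation of post-baseline HRQoL scores fails as a robustness check on either reading, even when data are missing completely at random. At about 14% missing, coverage falls to about 91% with own-arm means, or about 14% of the group difference is lost with a pooled mean. At the 10% threshold the corresponding figures are about 92% and 10%. The 14% rests on the assumption that HRQoL missingness follows the planned dropout. All the sizes rest on equal, random missingness in the two arms. This should be corrected, but it does not threaten the primary analysis or the available-values HRQoL result.

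**What to change.** In the HRQoL part of 3.2.1.2, name the mixed model on available data as the main HRQoL analysis, stating its missing-at-random assumption. In 3.2.10, delete mean imputation of post-baseline scores for both FACT-P and SF-36v2. When more than 10% of a score is missing, specify as the sensitivity analysis multiple imputation by arm, using baseline and earlier scores, with results combined so that imputation uncertainty enters the standard errors. It should include a delta-adjusted missing-not-at-random scenario with the shifts fixed in advance; without that scenario it would mostly repeat the main model. State whether the 10% is judged per visit, and give a separate rule for missing baseline scores.

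The cost is a few sentences in the SAP and a standard multiple-imputation program. No change to data collection is needed.
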